The primary analysis will be conducted using a logistic regression analysis with region, disease severity (IGA), age, treatment group, and treatment group-by-age interaction in the model. The p-value and 95% confidence interval (CI) for the odds ratio from the logistic regression model are used for primary statistical inference. The primary analysis will include data from the entire study population 2 to <18 years old, and a frequentist approach will be used for the analysis. However, in the event that the older subgroup of patients (10 to <18 years old) completes the Double-blind Treatment period (Study Period 3) more than 6 months earlier than anticipated for the younger subgroup of patients (2 to <10 years old), each age subgroup is adequately powered and can be individually unblinded and analyzed according to a pre-planned analysis approach as described in Section 10.3.8 below. This is to ensure that potential delay in completing the enrollment of the younger patients will not delay analysis and submission of the data from the older patients.

Sample size estimates were calculated using nQuery® Advisor 7.0 for the older subgroup of patients, and power estimates were obtained from R 3.5.0 and JAGS 4.2.0 for the younger subgroup of patients.

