10.3. Statistical Analyses

10.3.1. General Statistical Considerations

Statistical analysis of this study will be the responsibility of Lilly or its designee. A detailed SAP describing the statistical methodologies will be developed by Lilly or its designee.

Any change to the data analysis methods described in the protocol will require an amendment ONLY if it changes a principal feature of the protocol. Any other change to the data analysis methods described in the protocol, and the justification for making the change, will be described in the clinical study report (CSR). Additional exploratory analyses of the data will be conducted as deemed appropriate.

All tests of treatment effects will be conducted at a 2-sided alpha level of 0.05, unless otherwise stated (e.g., refer to Section 10.3.7.3). Treatment comparisons of discrete efficacy variables between baricitinib and placebo will be made using a logistic regression analysis with region, disease severity, age, treatment group, and treatment group-by-age interaction in the model. The percentages, difference in percentages, and 95% confidence interval (CI) of the difference in percentages will be reported. Treatment-by-age interaction will be added to the logistic regression model of the primary and key secondary variables as a sensitivity analysis. If this interaction is significant at a 2-sided 0.1 level, further inspection will be used to assess whether the interaction is quantitative (i.e., the treatment effect is consistent in direction but not size of effect) or qualitative (the treatment is beneficial for some but not all age groups). The p-value from the Fisher exact test will also be produced.

When evaluating continuous measures over time, a restricted maximum likelihood-based mixed-effects model of repeated measures (MMRM) will be used. The model will include treatment, age cohort, baseline severity, visit, and treatment-by-visit interaction, and treatment-by-age cohort interaction as fixed categorical effects and baseline score and baseline score-by-visit interaction as fixed continuous effects. Region may be included in the model if

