10.3.3. Efficacy Analyses

10.3.3.1. Primary Analyses

The primary efficacy measure is the binary outcome of response defined as IGA score of 0 or 1 (clear or almost clear skin) and ≥ 2 -point improvement from baseline at Week 16. The primary analysis will be conducted using a logistic regression analysis with region, disease severity (IGA), age, treatment group, and treatment group-by-age interaction in the model. Nonresponder imputation for missing data as described above will be used.

The primary analysis will include data from the entire study population 2 to <18 years old and will use a frequentist analysis approach. However, in the event that the older subgroup of patients (10 to <18 years old) completes the Double-blind Treatment period (Study Period 3) more than 6 months earlier than the anticipated completion for the younger subgroup of patients (2 to <10 years old), each age subgroup will be unblinded and analyzed separately according to a pre-planned analysis approach as described in Section 10.3.8 below. This is to ensure that potential delay in completing the enrollment of the younger patients will not delay analysis and submission of the data from the older patients.

Additional analysis of the primary efficacy outcome will include analyzing the outcome as observed, that is, whether or not rescue medication was used.

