10.3.3.2. Secondary Analyses

The following secondary categorical outcomes will be analyzed in a similar manner as the primary, that is, using the same logistic regression model. Nonresponder imputation will be used for these analyses unless otherwise noted.

- EASI75 at Week 16 and 1 year. EASI75 is defined as having an improvement of at least 75% from baseline. Besides NRI, this outcome will also be analyzed using observed cases, that is, whether rescue medication was given or not.
- EASI90 at Week 16. EASI90 is defined as having an improvement of at least 90% from baseline.
- EASI50 at Week 16. EASI50 is defined as having an improvement of at least 50% from baseline.
- SCORAD75 at Week 16 and 1 year. SCORAD75 is defined as having an improvement of at least 75% from baseline.
- SCORAD90 at Week 16. SCORAD90 is defined as having an improvement of at least 90% from baseline.
- IGA score of 0 or 1 (clear or almost clear skin) and ≥ 2 -point improvement from baseline at Week 4 and 1 year.

- IGA of 0 at 16 weeks.
- 4-point improvement in Itch NRS at 1 week, 2 weeks, 4 weeks, and 16 weeks.

The following continuous measures will be analyzed with the MMRM analysis described above unless otherwise noted. Contrasts within the MMRM analysis will be used to assess treatment differences for time points of interest as specified above in the list of objectives.

- Mean change from baseline in the following outcome measures:
 - ADSS Item 2
 - EASI score
 - SCORAD score
 - BSA
 - Itch NRS
 - Skin Pain NRS
 - POEM
 - PGI-S-AD
 - PROMIS-Depression
 - PROMIS-Anxiety
 - DFI
 - CDLQI and IDQOL total score
 - WPAI-AD-CG
 - EQ-5D-Y
 - PRISM

Baricitinib tablet or oral suspension product acceptability and palatability during the PK lead-in period will be summarized categorically (frequency and percentage) by age group, for each visit separately and in aggregate.

The EASI total score and SCORAD total score will also be analyzed as observed, that is, not assuming missing values after rescue medication is given.

The following categorical data will be analyzed using Fisher exact test described above unless otherwise noted.

- Patients requiring rescue with TCS
- Patients requiring rescue with systemic treatments
- School days missed

The following measures will be analyzed by an ANCOVA with treatment and baseline value in the model.

- Mean number of days without use of TCS over 16 weeks
- Mean gram quantity of TCS used over 16 weeks (tube weights)

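### The protocol puts the treatment-by-age interaction in the primary logistic model and also says it is only added as a sensitivity analysis

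*Protocol*

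**What the plan says.** Four places put the interaction in the logistic model:

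- Synopsis, Statistical Analysis, and Section 10.1, in the same words: "logistic regression analysis with region, disease severity (IGA), age, treatment group, and treatment group-by-age interaction in the model".
- Section 10.3.1, for discrete efficacy variables in general: "logistic regression analysis with region, disease severity, age, treatment group, and treatment group-by-age interaction in the model".
- Section 10.3.3.1, for the primary endpoint: "disease severity (IGA), age, treatment group, and treatment group-by-age interaction in the model".

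Section 10.3.3.2 extends this to the binary secondary endpoints, which are "analyzed in a similar manner as the primary, that is, using the same logistic regression model". That covers the binary key secondaries: EASI75, EASI90, SCORAD75 and the 4-point Itch NRS improvement.

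Two sentences after listing the term, Section 10.3.1 says: "Treatment-by-age interaction will be added to the logistic regression model of the primary and key secondary variables as a sensitivity analysis". It then sets a 0.1-level test, with further inspection if the interaction is significant.

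On inference, Section 10.1 says the p-value and 95% interval "for the odds ratio from the logistic regression model are used for primary statistical inference", and "The primary analysis will include data from the entire study population 2 to <18 years old". Section 10.3.8 makes the combined analysis secondary if the older cohort finishes Period 3 more than 6 months before the younger cohort is expected to.

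**The concern.** The sensitivity sentence makes sense only if the main model has no interaction. The other statements say that it has one. A statistician who follows Sections 10.1 and 10.3.3.1 and one who follows the sensitivity sentence would fit different primary models, and each could cite the protocol.

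Without the interaction, the model has one treatment odds ratio per dose, adjusted for age. With it, each dose has one odds ratio per age cohort, and an overall figure exists only once the cohorts are weighted. Section 10.1 names a single odds ratio for the whole population but not the contrast that yields it. At stake are the primary p-value and confidence interval for each dose, those of the binary key secondaries, and the freedom to choose between two documented models after the data are seen.

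**Working it through.** **Texts side by side.** The Synopsis and Sections 10.1, 10.3.1 (model list) and 10.3.3.1 put the term in. Section 10.3.1 (sensitivity sentence) adds it later, to the same primary and key secondary models. No passage distinguishes two different interaction terms or two stages of modelling.

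**Inputs from the protocol.** Response rates 10% placebo, 25% medium and 30% high; two-sided alpha 0.05; 440 patients at 1:1:1:1, so 110 per arm; at least 320 older and 120 younger, so 320/4 = 80 and 120/4 = 30 per arm.

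**Assumptions.** Age enters as the two cohorts (Section 10.3.7.3 divides age at 10 years). Response rates are the same in both cohorts. Each dose is compared with placebo by a Wald test. Age is not a stratification factor, so actual counts would vary.

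**The plan's own power figure.** For the chi-squared test, power = Φ[(|p2 − p1|√n − 1.96√(2p̄(1 − p̄))) / √(p1(1 − p1) + p2(1 − p2))] with n = 110.

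- High: (0.20 × 10.488 − 1.96 × √0.32) / √0.30 = 1.81, so 96.5%.
- Medium: (0.15 × 10.488 − 1.96 × √0.28875) / √0.2775 = 0.99, so 83.8%.

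The stated figure of over 95% reproduces for the high dose, but not for the medium dose alone. That is a separate matter. These values serve here as the no-interaction benchmark.

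**Why the contrast matters.** In a saturated treatment-by-cohort model, a cohort's log odds ratio has variance equal to the sum of 1/(responders) + 1/(non-responders) over its two arms. At expected counts for the medium dose:

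- Log odds ratio in each cohort: ln[(0.25/0.75)/(0.10/0.90)] = ln 3 = 1.099.
- Older variance: 1/8 + 1/72 + 1/20 + 1/60 = 0.2056.
- Younger variance: 1/3 + 1/27 + 1/7.5 + 1/22.5 = 0.5481.
- Weights 80:30: variance (80/110)² × 0.2056 + (30/110)² × 0.5481 = 0.1495, SE 0.387, z = 2.84.
- Common odds ratio, no interaction: 1/(1/0.2056 + 1/0.5481) = 0.1495, the same.
- Equal weights: (0.2056 + 0.5481)/4 = 0.1884, SE 0.434, z = 2.53.

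Sample-size weights therefore cost essentially nothing when the effect is the same in both cohorts. Equal weights raise the variance by 0.1884/0.1495 − 1 = 26%.

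**Simulation** (400,000 trials per dose, no other covariates; medium / high dose):

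| Primary model | Power, finite fits | Power, zero cells counted as failures | Significance differs from no interaction (finite fits) |
|---|---|---|---|
| No interaction | 84% / 97% | not applicable | – |
| Interaction, sample-size weights | 83% / 97% | 80% / 92% | 1.8% / 0.5% |
| Interaction, equal cohort weights | 73% / 92% | 70% / 88% | 13% / 6% |

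A zero cell occurs in 4.3% of trials. Nearly all are trials with no responder among the 30 younger placebo patients: 0.9^30 = 4.2%. Such a trial has no finite interaction estimate by ordinary maximum likelihood, hence the two power columns.

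**Covariates.** Adding severity and region (assumed: 40% IGA 4 with odds ratio 0.5 for response, three equal regions with no effect; 20,000 trials per dose) gave 84.5% / 96.9% without the interaction and 83.6% / 96.7% with sample-size weights in finite fits. The comparison does not change.

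**The case against.** The strongest reply is that the primary model is hardly in doubt. Four statements, including the dedicated primary-analysis section, include the interaction. The one sentence against them calls itself a sensitivity analysis and looks like a leftover. The choice of contrast also belongs in the SAP, to which Section 10.3.1 defers detail, and a sensible contrast changes very little.

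Much of this stands. The weight of the text favours the interaction, and a missing contrast alone would not be a finding. But the protocol states two incompatible main models, so a SAP that follows either departs from the other. An averaged contrast does give a single odds ratio, but sample-size and equal weights are both whole-population contrasts and differ materially.

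Three stronger readings are tempting and not supported:

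- A reader might take the treatment coefficient with the older cohort as reference, where power falls to 70.9% / 89.5% and significance differs in 17.0% / 8.1% of trials. That coefficient tests one cohort, and Section 10.1 says the primary analysis covers the whole population.
- A reader might treat age as continuous and take the coefficient at age 0. That lies outside the eligible ages, and Section 10.3.7.3 points to two age groups.
- A reader might extend the contradiction to the MMRM, which carries "treatment-by-age cohort interaction as fixed categorical effects". There the term is listed once and never called a sensitivity term, and Section 10.3.1 already bases the comparison on least squares means and contrasts within the model.

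**Conclusion.** The contradiction is real and should be fixed, because it concerns the model behind the primary odds ratio and p-value and, through Section 10.3.3.2, the binary key secondaries. It does not show that the trial is underpowered or that its primary result would be unreliable.

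Its size depends on the contrast. In finite fits, the interaction with sample-size weights costs at most about 1 point of power. Equal cohort weights cost about 84 − 73 = 11 points (medium) and 97 − 92 = 5 points (high). If trials with a zero cell count as failures, the corresponding losses are about 4/5 and 14/9 points.

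These figures rest on the 80/30 split, equal rates in both cohorts, two-level age and Wald tests. Primary inference is affected only if the cohorts are analysed together. On the split path in Section 10.3.8 the combined analysis is secondary.

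**What to change.** State one primary logistic model, in the same terms, in Section 1 (Synopsis), 10.1, 10.3.1 and 10.3.3.1. Either option works:

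- (a) Keep age as a main effect only in the primary and binary key secondary models, and fit treatment-by-age solely as the sensitivity and subgroup analysis.
- (b) Keep the interaction, as most of the text does. Delete the sentence that adds it as a sensitivity analysis, retain the 0.1-level inspection, and state that the primary odds ratio, confidence interval and p-value come from the treatment contrast weighted by the observed age-cohort sizes.

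If the SAP already fixes one of these, bring the protocol into line with it. The protocol does not show whether Period 3 has been unblinded. If it has, report the model specified before unblinding as primary and the other as sensitivity.

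The cost is text only, with no new data. Option (b) needs one sentence removed and one added in Section 10.3.1, with cross-references. Option (a) needs the interaction struck from the model statement in each of the four sections.

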10.2. Populations for Analyses

Unless otherwise specified, the efficacy and health outcome analyses will be conducted on the intent-to-treat population, defined as all randomized patients, even if the patient does not receive the correct treatment or otherwise did not follow the protocol. Patients will be analyzed according to the treatment to which they were assigned. Significant protocol violations will be described in the SAP.

Safety analyses will be performed for all randomized patients who received at least 1 dose of IP and who did not discontinue from the study for the reason “Lost to Follow-up” at the first postbaseline visit.

Safety analyses for the Post-treatment Follow-up period will be conducted on the follow-up population, defined as all randomized patients who received at least 1 dose of IP and entered the Post-treatment Follow-up period. Patients will be analyzed according to the dosing regimen to which they were assigned in the Treatment Period.

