
 To assess efficacy of baricitinib during longer-term treatment. 	
 Proportion of patients achieving IGA of 0 or 1 with a ≥ 2-point improvement at 1 year Proportion of patients achieving EASI75 at 1 year Proportion of patients achieving SCORAD75 at 1 year

 To assess growth and bone safety of baricitinib during longer-term treatment. 	
 Mean changes in growth (height and weight), growth velocity, and bone age over the course of treatment during the long-term extension treatment period
Tertiary/Exploratory Objectives	

 Frequency of patient-reported “no itch” (Itch NRS score = 0) days from daily diaries from Week 12 to Week 16 Frequency of patient-reported “no pain” (Skin Pain NRS score = 0) days from daily diaries from Week 12 to Week 16 Time to achieve a 4-point improvement in Itch NRS Mean change from baseline in the score of Item 1 of the ADSS at 1 week and 16 weeks Mean change from baseline in the score of Item 3 of the ADSS at 1 week and 16 weeks To evaluate changes from baseline in IgE levels during the study To evaluate changes from baseline in eosinophil levels during the study To characterize baricitinib pharmacokinetics in the AD population and explore relationships between baricitinib exposure and study endpoints Assessment of efficacy outcomes in patients who choose to take a voluntary drug interruption (drug holiday) during Study Period 4 Number of patients able to maintain control of AD signs and symptoms without use of TCS Proportion of patients achieving IGA of 0 or 1 with a ≥ 2-point improvement at 2, 3, 4, and 5 years during long-term extension Proportion of patients achieving EASI75 at 2, 3, 4, and 5 years during long-term extension Proportion of patients achieving SCORAD75 at 2, 3, 4, and 5 years during long-term extension 	

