5.1.3. Period 3: Double-blind Placebo-Controlled Treatment Period

General enrollment into Study Period 3 will begin for an age group only after analysis of the PK lead-in data for the specific age group confirms appropriate dose selection. Patients who participated in the PK lead-in will not participate in Study Period 3.

Patients who will participate in the double-blind treatment period (Study Period 3) will continue using Sponsor-provided low- and medium-potency TCS as clinically indicated and determined by the investigator. At Visit 2 (Week 0, baseline), study eligibility for each patient will be reviewed, based on all inclusion and exclusion criteria (Sections 6.1 and 6.2, respectively) and laboratory test results. Patients who meet all of the inclusion criteria and none of the exclusion criteria will proceed to randomization and begin the 16-week double-blind, placebo-controlled treatment period (Figure JAIP.2).

At Visit 2, after laboratory samples are collected and all assessments are completed, patients will take the first dose of investigational product (IP) at the clinic and PK samples will be drawn 15 minutes and 1 hour postdose. Pharmacokinetic sampling and the related timing of dosing for IP for each visit are detailed in Section 9.5.

Patients will be randomized at a 1:1:1:1 ratio into 1 of the 4 treatment groups (placebo QD, baricitinib low dose QD, baricitinib medium dose QD, or baricitinib high dose QD). Investigational product will be administered daily for 16 weeks (treatment period Visits 2 through 8). All patients will be required to use emollients daily. Daily diaries will continue to be utilized throughout the treatment period. The use of low- and medium-potency TCS, TCNIs, and phosphodiesterase type 4 (PDE-4) inhibitor for the treatment of AD is allowed as background treatment as described in Section 7.7.1. High- and ultra-high-potency TCS and systemic therapies may be used as rescue treatment during Study Period 3 (details of rescue therapy and criteria are included in Section 7.7.5). Assessments of disease severity will be performed by the investigator at all study visits including unscheduled and early termination visits (ETVs).

The primary efficacy endpoint and final visit in the treatment period will be at Week 16 (Visit 8). Patients who complete through the Week 16 study visit will be eligible to continue in the Long-term Extension period for up to 5 additional years of treatment.

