5.1.4. Period 4: Long-term Extension Treatment Period

PK Lead-in Patients:

Patients participating in the PK lead-in period (Study Period 2) may proceed to the Long-term Extension period (Visit 9) 2 weeks after completing Visit 4 and continue to receive open-label baricitinib at the same dose they received in the PK lead-in. Patients may continue in the long-term extension for up to an additional 5 years (Figure JAIP.3).

Non-PK Lead-in Patients:

Patients who participate in the Double-blind Treatment period (Study Period 3) and complete through Week 16 (Visit 8) will be eligible to continue in the Long-term Extension period for up to 5 additional years of treatment (Figure JAIP.3). At Visit 8 (primary endpoint and end of the double-blind period), patients will be transitioned into the long-term extension treatment period as follows:

- Patients randomized to Double-blind Treatment who have achieved a response of IGA 0, 1, or 2 at Visit 8 (Week 16) without requiring rescue with topical treatments or systemic treatments during Study Period 3 will continue on the Double-blind Treatment to which they were randomized at Visit 2 (Week 0).

- Patients randomized to Double-blind Treatment who have not achieved a response (i.e., IGA of ≥ 3) or who have required rescue with topical treatments (i.e., high-/ultra-high-potency TCS) or systemic treatments during Study Period 3 will be transitioned to open-label baricitinib at the high dose for their age group.

All Patients:

During Study Period 4, patients are allowed to use TCS (all potencies), TCNI, and/or a PDE-4 inhibitor (e.g., crisaborole) as background treatments with IP if they experience worsening or lack of control of their AD.

During the first year of the extension treatment, use of background TCS, TCNI, and PDE-4 inhibitors is allowed as described in Section 7.7.2. During Study Period 4, for patients on double-blind treatment whose IGA worsens to 3 or 4 and who are unable to recapture an IGA response of 0, 1, or 2, despite the use of emollients and TCS, the patient may be transitioned at the discretion of the investigator to open-label baricitinib at the high dose for their age group.

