7.2. Method of Treatment Assignment

Patients participating in the PK lead-in who meet all criteria for enrollment will receive open label baricitinib at the high dose for their age group beginning at Visit 2.

Patients not participating in the PK lead-in who meet all criteria for enrollment will be randomized in a 1:1:1:1 ratio (placebo, baricitinib low dose; baricitinib medium dose; baricitinib high dose) to double-blind treatment at Visit 2. Assignment to treatment groups will be determined by a computer-generated random sequence using an interactive web-response system (IWRS). The IWRS will be used to assign blister packs or bottles containing double-blind IP to each patient according to the Study Schedule (Section 2). Site personnel will confirm that they have located the correct blister packs or bottles by entering a confirmation number found on the blister packs or bottles into the IWRS.

Randomization will be stratified by disease severity at baseline (IGA 3 versus 4) and geographic region if the planned country allocation justifies. Definitions of geographic regions and plan for analysis by region will be described in the SAP.

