10.3.4. Safety Analyses

All safety data will be descriptively summarized by treatment group and analyzed using the safety population.

Treatment-emergent adverse events (TEAEs) are defined as AEs that first occurred or worsened in severity after the first dose of study treatment. The number and percentage of patients who experienced at least 1 TEAE will be summarized using MedDRA (Medical Dictionary for Regulatory Activities) for each Preferred Term within System Organ Class by treatment group. Serious adverse events and AEs that led to permanent discontinuation from the IP will also be summarized by treatment group. Special safety topics will be summarized and analyzed including the proportion and rate of patients developing skin infections requiring antibiotic treatment. Fisher’s exact test will be used to perform comparisons between each baricitinib dose and the placebo group, where applicable.

Clinical laboratory results will be descriptively summarized by treatment group. Individual results that are outside of normal reference ranges will be flagged in data listings. Quantitative clinical laboratory variables obtained at baseline and postbaseline visits will be summarized along with change from baseline by treatment group. Change from baseline to endpoint will be analyzed using ANCOVA with treatment and baseline value in the model. Categorical variables, such as treatment-emergent laboratory abnormalities, will be summarized by frequency and percentage. Shift tables will be presented for selected laboratory measures.

Observed values and changes from baseline for vital signs and physical characteristics will be descriptively summarized by treatment group and time point. Change from baseline to postbaseline in vital signs, height, and body weight will be analyzed using ANCOVA with treatment and baseline value in the model. Treatment-emergent abnormalities in vital signs (pulse and blood pressure) and weight will be evaluated based on pediatric standards.

A summary of temporary interruptions of study drug will be provided, showing the number of patients experiencing at least one temporary interruption and the number of temporary interruptions. Duration of each temporary interruption and the cumulative duration of interruptions using descriptive statistics will be provided.

Analyses of Growth (height, weight, and body mass index [BMI]):

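### Post-treatment follow-up safety is grouped by the assigned regimen, so patients who switched to open-label high dose would be counted under placebo, low or medium dose after stopping high dose

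*Protocol*

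**What the plan says.** Protocol Section 10.2 defines the follow-up population as "defined as all randomized patients who received at least 1 dose of IP and entered the Post-treatment Follow-up period", and fixes its grouping: "Patients will be analyzed according to the dosing regimen to which they were assigned in the Treatment Period". No section groups follow-up safety by the last regimen received or by treatment sequence.

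The surrounding text points to the randomised arm. Assignment is the Visit 2 randomisation (Section 7.2: "Assignment to treatment groups will be determined by a computer-generated random sequence using an interactive web-response system (IWRS"). In Section 5.1.3 the treatment period runs from Visit 2 to Visit 8 ("The primary efficacy endpoint and final visit in the treatment period will be at Week 16 (Visit 8"). Later changes of treatment are described as transitions.

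Those transitions come before follow-up. At Visit 8, randomised patients with IGA of 3 or more, or with Period 3 rescue, "will be transitioned to open-label baricitinib at the high dose for their age group", whatever their arm. For patients still on double-blind treatment who lose response and cannot recapture it, "the patient may be transitioned at the discretion of the investigator to open-label baricitinib at the high dose for their age group". Section 7.7.5.2 repeats both rules. Under Section 5.1.5, Visit 801 takes place about 28 days after the last dose, both for patients who stop at Week 16 and for those who complete the extension.

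**The concern.** The follow-up period exists to observe safety once the drug is stopped (Section 5.4), so the relevant exposure is what the patient was taking before stopping. For a patient who switched, the randomised arm does not describe it. A child who took placebo for 16 weeks and then high dose through the extension would appear in the placebo column in the weeks after stopping high dose. Switchers from the low and medium arms are misplaced in the same way. Switchers from the high arm are not affected, because they stay on the same dose.

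The placebo, low and medium columns would therefore hold some patients coming off high dose. Any difference between those columns and the high-dose column would be pulled towards zero, which is the unhelpful direction for a safety summary.

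**Working it through.** The protocol gives no figure for this rule, so there is nothing to reproduce. The check has two parts.

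**Which regimen the sentence means**

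1. Randomised-arm reading (Sections 7.2 and 5.1.3): the rule is clear, but it misplaces everyone who switched out of placebo, low or medium dose.
2. Reading that includes Period 4: Period 4 is itself titled as an extension treatment period, and Table JAIP.4 lists open-label high dose as a regimen for it. A switcher then has two regimens, and the sentence does not say which one counts.

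The sentence needs correction on either reading.

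**Effect under the randomised-arm reading**

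Inputs:
- r0: follow-up event rate in patients coming off placebo (not in the protocol).
- r1: follow-up event rate in patients coming off high dose (not in the protocol).
- s: share of the placebo arm's follow-up patients who switched to high dose (not in the protocol).
- Assumption: switchers carry the rate r1.

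Formulas:
- Rate shown in the placebo column = (1 - s) × r0 + s × r1.
- Apparent difference = r1 - [(1 - s) × r0 + s × r1] = (1 - s) × (r1 - r0).

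The fraction of the true difference that remains is 1 - s, whatever the event rates. The table adds assumed rates r0 = 2% and r1 = 10% (true difference 8.0 points) for illustration only.

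| s (assumed) | Placebo column shows | Apparent difference | Share of true difference |
|---|---|---|---|
| 0% | 2.0% | 8.0 points | 100% |
| 25% | 0.75 × 2 + 0.25 × 10 = 4.0% | 6.0 points | 75% |
| 50% | 0.50 × 2 + 0.50 × 10 = 6.0% | 4.0 points | 50% |
| 70% | 0.30 × 2 + 0.70 × 10 = 7.6% | 2.4 points | 30% |

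The low and medium arms follow the same formula, each with its own share and rate.

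**What the protocol says about s.** Section 10.1 assumes a 10% placebo response on IGA 0 or 1. The other 90% is only a ceiling on switching at Week 16, because patients with IGA 2 and no rescue stay double-blind. It is also a share of the randomised arm, whereas s is a share of those who enter follow-up.

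**The case against.** The strongest objection is that the protocol never defines the term Treatment Period, so the randomised-arm reading is an inference. That is fair. Sections 7.2 and 5.1.3 favour that reading without settling it. But the other reading does not rescue the rule, since it leaves switchers with no determinate group.

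Second, the affected summary is small: about 28 days off drug, with no test specified for follow-up in particular, and Fisher comparisons in Section 10.3.4 made only where applicable. That limits the weight of the point. It does not make the attribution right.

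Third, grouping by last regimen has its own bias. Switching is triggered by poor response or rescue. Among extension patients, those still on placebo are selected for response, and the high-dose group gains the treatment failures. This stands, and it is why the regrouped figures should be descriptive.

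A reader might also infer more than the protocol supports:

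- *That growth and bone findings would be diluted.* The Section 10.2 sentence governs follow-up only. The schedules show no height and no hand or knee x-ray at Visit 801, and Section 10.3.4 sets height velocity against age- and sex-matched reference tables, not against placebo.
- *That extension safety in Section 10.3.4 has the same fault.* That section says "All safety data will be descriptively summarized by treatment group and analyzed using the safety population" and does not say that extension data follow the randomised arm. It leaves further detail to the SAP.
- *That the number misplaced can be calculated.* It cannot. Patients who need biologics may not enter Period 4 (Section 7.7.5.1). Those who stay in the study more than 28 days after discontinuing IP do not need Visit 801, and others will leave.

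**Conclusion.** The point holds for post-treatment follow-up safety. Followed as written, and on its most natural reading, Section 10.2 counts events after stopping open-label high dose under placebo, low or medium dose for patients who switched. On the alternative reading it does not say where they belong. This is a rule the protocol states, not a detail it leaves to the SAP.

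The effect is a shrinkage of the high-minus-placebo difference to (1 - s) of its true size, provided switchers carry the high-dose event rate. The retained shares of 75%, 50% and 30% are illustrations at assumed values of s; the protocol supports no estimate. The misattribution is confined to switchers from the placebo, low and medium arms. Patients who leave at Week 16, or stay double-blind to the end, are correctly classed. The conclusion does not extend to the growth and bone objective or to the extension-period analyses.

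**What to change.** In Section 10.2, replace the grouping sentence with one of the following:

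- follow-up safety is analysed by the regimen received at the last dose before follow-up; or
- follow-up safety is analysed by treatment sequence, meaning the randomised arm, then open-label high dose yes or no.

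Keep the randomised arm as a supportive presentation. The sequence version keeps the randomised arm visible and shows the switchers separately.

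The cost is protocol and SAP wording plus some programming, with no change to treatment, visits or data collection. The schedules list the IWRS at every visit, so each patient's regimen history should be recoverable, although the protocol does not say that switch dates are held there. The downside is that the groups are not randomised and are selected by response, so the text should say that they are read descriptively.
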